**ABSTRACT:**

**Background:** The essential micronutrient zinc balances immune responses to infections and additionally directly inhibits some viruses. We have recently shown a robust correlation between serum zinc levels (SZL) and COVID-19 outcome in patients and a direct effect of zinc levels on SARS-CoV-2 expansion in cell culture. These results suggest that SZL might represent an important risk factor for COVID-19 severity whose adjustment would constitute an early and cost-effective therapeutic intervention.

**Objectives:** To explore the therapeutic benefit of zinc supplementation for COVID-19 patients and to determine the cellular and molecular basis of the effect of zinc levels on SARS-CoV-2 infections.

**Methodology:** A randomized clinical trial supplementing COVID-19 patients with zinc will be carried out and viral loads, inflammatory and novel zinc-related clinical markers and SARS-CoV-2-specific T- and B-cell Responses monitored. Humanized-ACE2-mice models will be used to address causal-effect associations between zinc levels and SARS-CoV-2 infection. Infections of human Calu-3 cells will be used to decipher the direct antiviral action of zinc on SARS-CoV-2 life cycle.

**Expected results:** We will generate a clear insight into zinc functioning in COVID-19 patients that might provide a therapeutic guideline immediately applicable to reduce the severity of SARS-CoV-2 pathogenicity and possibly other virus infections.

**LAY SUMMARY:**

Infections with SARS-CoV-2 result in a systemic disease with a variety of outcomes, from no symptoms to severe and diverse pathologies. Therefore, it is important to identify risk factors determining COVID-19 severity, especially if those factors might be adjusted, allowing early and effective therapeutic interventions.

Zinc is a trace element essential for human health. Zinc deficiency is common in old adults, vegetarians and patients with chronic inflammatory diseases. This condition causes immune dysfunction leading to increased risk of inflammatory and infectious diseases, including acquired immune deficiency syndrome, measles, malaria, tuberculosis, and pneumonia. Besides, zinc has a direct antiviral activity against specific viruses like rhinovirus, HCV, herpes simplex virus. In this scenario, it has been shown that zinc supplementation has benefits on the recurrence and persistence of acute and chronic viral infections like common cold or HCV, HBV. Moreover, our team has recently done an observational study with 249 COVID-19 patients that showed how COVID-19 patients with lower plasma zinc content had worse prognosis, increased time of hospitalization and mortality.

Therefore, the main aim of the project is to explore the therapeutic benefit of zinc supplementation for COVID-19 patients and to determine the cellular and molecular basis of the effect of Zn levels on SARS CoV-2 infections. For that purpose we will run a clinical trial supplementing with zinc COVID-19 patients. Moreover, we will carry out experiments to understand the association between zinc nutritional status and SARS-Cov-2 infection progression in cellular and animal models.

Given the current knowledge about zinc supplementation toxicity and dosage, we expect that recommendations derived from this study will be rapidly applied by physicians and public health decision makers. The results of these studies will be used as a guideline to administer zinc supplements in COVID-19 patients in order to reduce disease severity and mortality. Moreover, our experiments will clarify whether zinc supplementation as a prophylaxis strategy is useful to protect the population at risk of zinc deficiency, more than 20% worldwide.

Finally, considering the new knowledge that this project will generate about the role of zinc in immune responses and viral expansion, we expect that our results will help researchers and physicians to design novel strategies to boost specific immune cell subpopulations against SARS-CoV2 infection. Thus, this knowledge could be used long-term for designing medicines against SARS-CoV-2 and other viral infections.

- **HYPOTHESIS AND DESCRIPTION OF THE PROJECT OBJECTIVES**

We hypothesize that low zinc nutritional status has an impact on COVID-19 progression and that adjustment of this status might constitute an early therapeutic intervention point by balancing immune responses and acting as an antiviral agent. This hypothesis is supported by the following observations:

- Zinc nutritional status impacts on innate and adaptive immunity and influences inflammatory markers(4).

- Zinc has a direct antiviral activity against specific viruses like rhinovirus, HCV, SARS-CoV(16).

- Zinc supplementation has benefits on the recurrence and persistence of acute and chronic viral infections like common cold, or HCV, HBV (2,6) and reconstitutes the production of interferon-alpha from elderly persons(16).

-Our recent data in a cohort of 249 COVID-19 patients show that COVID-19 patients with lower plasma zinc content have worse prognosis, increased time of hospitalization and mortality and that Zn and IL-6 levels are negatively correlated (13). However, the cause-effect association between nutritional zinc status and COVID-19 inflammatory response remains unproven,

-Our recent data in cell culture studies show that low zinc levels correlate with higher SARS-CoV-2 expansion(13).

The main aim of the project is to explore the therapeutic benefit of Zn supplementation for COVID-19 patients and to determine the cellular and molecular basis of the effect of Zn levels on SARS CoV-2 infections. To address these questions, we propose the following aims:

- **To study the impact of zinc supplementation on COVID-19 progression. There are two specific objectives:**

- **To carry out the clinical trial with COVID-19 patients (Subproject 1):**

We will run a randomized clinical trial with 60 COVID-19 patients admitted at Hospital del Mar with a control and a zinc supplementation group.

- **To study the immune responses of the COVID-19 patients enrolled in the clinical trial (Subproject 2):** Viral loads, zinc homeostasis markers and T- and B-cell populations in PBMC from COVID-19 patients in control and zinc supplemented groups will be determined. Disease progression and clinical outcomes will be evaluated.

- **To establish causal-effect associations between zinc levels and SARS-CoV-2 infections (Subproject 3):** We will monitor viral expansion and immune responses in SARS-CoV2 infected

hACE2-mice with different zinc nutritional status (i) to evaluate whether SARS-Cov-2 induces changes in SZL and (ii) to study prophylaxis and therapeutic properties of zinc supplementation.

- **To characterize novel zinc homeostasis reporters upon SARS-CoV2 infection (Subproject**

**2)** We will characterize the expression of zinc transporters and metallothioneins in PBMC from COVID-19 patients and mice infected with SARS-CoV-2.

- **To decipher the direct antiviral action of Zn on SARS-CoV-2 life cycle steps**

**(Subproject 2)** Infections of human Calu-3 cells will be used to decipher the direct antiviral action of Zn on SARS-CoV-2 life cycle steps. Moreover, zinc homeostatic machinery will be evaluated upon infection.

## **2. BACKGROUND AND STATE OF THE ART, INCLUDING RELEVANT BIBLIOGRAPHY**

Zinc is a trace element essential for human health. Zinc deficiency (ZD) causes impaired body growth, neurological disorders, and immunosuppression leading to morbidity and increased risk of inflammatory and infectious diseases including acquired immune deficiency syndrome, measles, malaria, tuberculosis, and pneumonia (1,2). The human body contains 2–3 g of zinc, 0.1% of which are exchanged daily. Due to the lack of major storage organs of this mineral, the body needs a continuous nutritional supply. Zinc deficiency is considered a major public health problem in developing countries, especially in groups with low zinc intake as well as those with inhibited absorption due to high levels of phytates and fiber in vegetable-based diets. Besides, old adults, vegetarians, and people with gastrointestinal disorders are also considered to be at risk

for hypozincemia(1, 2). Globally, one third of the world population is at risk of mild ZD associated disorders. In the elderly, the incidence ranges from 15 to 31% depending on the age and the country of study (3). Remarkably, older adults are the group at higher risk for severe symptoms and mortality from COVID-19. In this context, ZD might be one of the important underlying factors of COVID-19 heterogeneity.

### **Cellular zinc homeostasis**

Zinc is a structural component of up to 10% of the proteome. Moreover, zinc participates as a second messenger in cell signalling. Zinc binding proteins and 24 zinc transporters work in a coordinated way to tightly regulate cytosolic zinc fluxes. There are two main families of zinc transporters, ZnT and Zip, which extrudes and enters zinc in the cytosol respectively (1). Within each zinc transporter family, the different members vary in cellular localization, affinity, selectivity, regulation and tissue expression. The expression and function of specific transporters is essential for the function and modulation of immune cells of adaptive and innate immunity (4).

The concentration of free zinc in the cytosol is not only determined by the activity of all these transporters but also by the quenching effects exerted by metallothioneins (MTs), abundant cytosolic proteins that quench metal ions, mainly zinc. These proteins, by releasing zinc, participate actively in the defense against reactive oxygen species (ROS). In humans, there are 4 MTs. Interestingly, the cellular expression of MTs is stimulated by

increases in cytosolic zinc content. In fact, one of the most reliable tests to measure the body zinc content is by measuring MTs expression in leukocytes (5).

### **Zinc and immune cells**

Early studies of zinc deficiency showed that zinc is essential for immune system function (4). Due to its importance for proper immune function, zinc supplementation and fortification programs have been widely carried out for boosting the immune system in populations at risk of ZD. Several clinical trials have proven that zinc supplementation is effective in certain types of viral and bacterial infections (reviewed in (2,6)).

### **Zinc and inflammation**

ZD is known to be associated with proinflammatory responses at infection, showing higher ROS production and inflammatory markers (6,7). An imbalance in cytokine production by cells of both innate and adaptive immunity has also been reported.

Concretely, ZD is associated with higher levels of IL-6, IL-1beta and TNF-alfa (6). In this scenario, zinc supplementation has been shown to decrease the incidence of infection, inflammatory cytokines, including IL-6, and oxidative stress markers in elderly individuals (7,8). Moreover, zinc supplementation has been shown to balance immune responses (9). Remarkably, IL-6 is a key player in COVID-19 patients by triggering severe lung damage during SARS-CoV-2 infection.

Sustained IL-6 promotes immune-mediated lung damage and macrophage activation syndrome (10). Nutritional zinc status and IL-6 are highly interconnected. Thus, IL-6 can reduce zinc bioavailability promoting internalization in hepatocytes and the expression of zinc chelators (11). On the other hand, zinc decreases IL-6 production via inhibition of STAT-3 pathway (12). Our study with COVID-19 patients showed a negative correlation between serum zinc levels and IL-6 production (13). Both parameters were robustly associated with COVID-19 progression. This data is in agreement by another observational study with a smaller cohort (14). However the cause-effect association between zinc status and inflammation markers in COVID-19 patients is not yet clear given the observational nature of the studies (13,14).

### **Zinc in viral infection**

Zinc is an essential trace element for both host and pathogens. In order to grow, pathogens require zinc. Thus, zinc is a structural cofactor of viral proteins and certain viruses have developed strategies to alter cellular zinc homeostasis on its benefit (15). On the other hand, there is extensive evidence that zinc can prevent viral replication and lower cellular invasion (eg. Rhinovirus, HCV, SARS-CoV) (reviewed in 6, 16).

Remarkably, our team has shown that low zinc levels favour SARS-CoV2 expansion (13). These results might indicate either a direct anti-viral action against SARS-CoV2 or that the virus benefits from stress conditions caused by low levels of cellular zinc. Although there are several evidences showing that zinc deficiency leads to increased susceptibility to certain infections, supplementation of zinc in viral infections has not always been seen

as beneficial. For example, zinc supplementation in HIV patients does not improve T-cell counts or reduces viral load. In contrast, zinc supplementation has been shown to be beneficial when administering to HBV and HCV infected patients. Moreover, zinc- based nutritional immunity reduces diarrheal episodes and respiratory track diseases (reviewed in 6,16). Remarkably, zinc supplementation for the common cold caused by rhino- and coronaviruses prevents it and reduces its duration, if the administration starts within 24h after the onset of symptoms (reviewed in 6,16). Thus, zinc supplementation has been proven beneficial against some viral infections. However, whether this was caused by improved local immune response or viral inhibition remains uncertain.

IFNs are key antiviral mediators of the host's immune response. Impaired IFN responses related to aging have been associated with increased susceptibility during certain viral infections. Older adults are more susceptible than younger adults to death resulting from viral infections due to a decline in interferons production. Interferons are antiviral agents produced by the host upon infection. Importantly, zinc supplementation reconstitutes the production of interferon-alpha by leukocytes from elderly persons (17). This is an important aspect when considering zinc based nutritional immunity

because SARS-CoV-2 has been shown to antagonize proinflammatory signals during early infection, particularly type I IFN (IFN-I) signaling. In fact, errors of immunity that diminish IFN-I activity are more commonly detected in patients with severe COVID-19 (18).

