### **Study Endpoints**

#### **Primary Endpoints**

- Number of days since admissions to clinical recovery
- Change in IL-6 levels from baseline to Week 2.
- Percentage of patients with disease progression by Week 2 based on WHO 9-point ordinal scale

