### **Study Design**

This is a randomized, open-label clinical study evaluating the effectiveness of zinc supplementation as compared to standard of care on need disease severity and on IL-6

levels in people with COVID-19. Subject eligibility will be based on inclusion and exclusion criteria

**Population of study:** Sixty eligible adult subjects at one clinical site in Spain (Hospital del Mar) will be randomized in a 1:1 ratio to:

- ~~Zinc acetate 80mg QD~~ 83.91 mg zinc acetate (Zinc+NM) QD + standard of care for 2 weeks
- Standard of care for 2 weeks

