### **Task 1.1.1 Visits and sample collection**

1.- Visit 1. Screening. Randomization. Baseline. Phase / Visit 0 or 1 ( Day 1 or up to 1 day  
Prior to Baseline/Randomization; In Person)

Visit performed at admission (+1). Written informed consent obtained. Medical history.  
Vital signs assignment. Clinical labs (CBC, CMP, CRP, ferritin, D-dimer,IL-6, zinc)

2.-Visit 2 / Week 1 (Day 7  $\pm$  2 days)

A complete record of AEs and concomitant therapies will be taken into account. 3.-

Visit 3 / Week 2 (Day 14  $\pm$  2 days), End of Treatment

A complete vital sign assessment (sitting blood pressure, heart rate, respiratory rate, O2  
sat, and oral temperature) review and record AEs and concomitant therapies, clinical  
labs (stated above) and PBMCs. Collect blood samples for future studies.

4.-Visit 4 / End of Study (Day 28  $\pm$  4 days)

Clinical labs (stated above) and PBMCs. Collect blood samples for future studies.

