### **Statistical analysis**

**Randomization: Subjects** will be randomized in a 1:1 ratio to:

- 83.91 mg zinc acetate (Zinc+NM) QD + standard of care for 2 weeks
- Standard of care for 2 weeks

**Determination of sample Size:** Sample size calculations are aimed at comparisons of days to clinical recovery between zinc supplementation and standard of care alone. Assuming alpha = 0.05 and a 10% dropout rate, randomization of 60 subjects will

provide 80% power to detect a difference in time to recovery between arms of 3 days assuming a SD of 4 days. This sample size will also provide at least 80% power to detect a change in percentage of people with clinical progression of 5% based on an estimated

clinical progression rate of 20% in the standard of care arm.

**Analysis Populations:** The analysis population for efficacy will be per protocol which includes all randomized subjects who complete 2 weeks of therapy and/or return for Week 2 visit. All safety analyses will include all randomized subjects who are

administrated at least 1 packet of the investigational product.

**Baseline Characteristics:** Demographics and Baseline characteristics will be summarized descriptively by group and overall using per protocol population. The following Baseline

characteristics will be summarized: sex, race, age, comorbidities, ethnicity

**Clinical Laboratory Assessments:** Blood chemistry, hematology parameters will be summarized at Baseline as well as visit 3 and 4. Laboratory values at Baseline and subsequent changes in laboratory values will be summarized descriptively overall and

by therapy group.

**Vital signs:** Vital sign measurements will be summarized at Baseline, Week 2 and Week 4. In addition, changes from Baseline to Week 2 or 4 will be summarized. For each summary the number, mean, median, standard deviation, minimum, and maximum

values will be presented overall and by therapy group.

**Safety Analyses:** All safety analyses will be based on the Safety Population, comprising all subjects who are randomized to the therapy group and subsequently receive at least one packet of investigational product. Safety assessments will be analyzed by frequency of events/abnormalities for categorical values or summarized using descriptive statistics

(mean, standard deviation, median, range, and number of observations).

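### Time since symptom onset is not a specified baseline item or covariate, yet the plan reads a null result as settling what low zinc means

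*Combined protocol and SAP*

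**What the plan says.** The section on zinc in viral infection reports that, for colds caused by rhino- and coronaviruses, zinc "prevents it and reduces its duration, if the administration starts within 24h after the onset of symptoms". The hypothesis section proposes that "adjustment of this status might constitute an early therapeutic intervention point", and does not define the word early. The preliminary results call for supplementing low-zinc patients at admission.

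Under Study phases, zinc starts on Day 1, the day of baseline and randomisation. Task 1.1.1 places that visit at admission, with a one-day allowance. The printed inclusion and exclusion criteria set no limit on symptom duration; further detail on exclusions is said to be in an Ethics Committee document that was not supplied. The first primary endpoint is "Number of days since admissions to clinical recovery".

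Visit 1 includes a medical history, but symptom-onset date is not a named item. In the Statistical analysis section, the baseline "characteristics will be summarized: sex, race, age, comorbidities, ethnicity". Neither the randomisation text nor any analysis paragraph uses time since onset.

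The Limitation paragraph that closes the trial's statistical text says that finding no benefit would mean the low zinc seen in patients with worse prognosis is a consequence of their inflammatory state.

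**The concern.** Patients reach hospital at different points in the illness. Days from admission to recovery probably depend in part on how far the illness has already run, and the plan's common-cold evidence makes it plausible that the effect of zinc does too. As written, the trial need not be able to say how long after onset its patients were treated, or whether the arms were alike in this respect.

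Two things are at stake. The first is interpretation: if zinc shows no benefit, treatment too late in the illness is a rival explanation that comes from the plan's own background, and the Limitation paragraph leaves no room for it. The second is precision: any variation in recovery time that days since onset explain stays in the error term of a small trial.

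**Working it through.** **1. The plan's own figure.** The sample-size paragraph takes an alpha of 0.05 and a loss of 10%, and holds that 60 patients would "provide 80% power to detect a difference in time to recovery between arms of 3 days assuming a SD of 4 days". Allocation is 1:1. The sidedness of alpha is not stated and is taken as two-sided.

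- Normal approximation: n per arm = 2 × [4 × (1.960 + 0.842) / 3]² = 27.9, so 28 per arm and 56 in total.
- Dropout: 56 × 1.10 = 61.6, so 62; or 56 / 0.90 = 62.2, so 63. The plan has 60.
- With 60 randomised and 10% lost, 27 per arm are evaluable. Power is 78.7% by the normal approximation and 77.2% by the noncentral t.

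The stated 80% is reproduced closely enough to use as the starting point.

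**2. Gain from adjusting for days since onset.** If days since onset correlate r with days to recovery, the residual SD is 4 × √(1 − r²), the standard error of the arm difference is that SD × √(2/27), and power follows from the noncentral t. The documents give no r, so the range is assumed.

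| Assumed r | Residual SD (days) | SE (days) | Power for 3 days |
|---|---|---|---|
| 0 (unadjusted) | 4.00 | 1.089 | 77.2% |
| 0.1 | 3.98 | 1.083 | 77.6% |
| 0.2 | 3.92 | 1.067 | 78.8% |
| 0.3 | 3.82 | 1.039 | 80.9% |
| 0.4 | 3.67 | 0.998 | 83.9% |
| 0.5 | 3.46 | 0.943 | 87.8% |

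The degree of freedom spent on the covariate changes these figures by less than 0.1 point.

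**3. Could the trial test whether earlier start matters if onset were recorded?** Take 54 evaluable patients, a fraction f of them early starters, equal arms within each group, and an assumed early-minus-late difference in effect of 3 days. Then SE = 4 × √[4/(54f) + 4/(54(1 − f))].

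- f = 0.50: SE 2.18, power 28%
- f = 0.25: SE 2.51, power 22%
- f = 0.10: SE 3.63, power 13%

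So an estimate of treatment effect by time since onset can only be exploratory.

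**4. Is adjustment useful for progression?** The plan assumes 20% progression under standard of care and a change of 5 points. Taken as a reduction to 15%, expected events are 27 × 0.20 + 27 × 0.15 = 9.45, or about 9 to 10. That is too few for covariate adjustment to be worth requiring.

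**5. The reading of a null.** The Limitation paragraph moves from no benefit to low zinc being a consequence of inflammation. That step needs other explanations to be excluded. The background offers one, start too late after onset, and no specified data item would let the investigators even describe it.

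**The case against.** The strongest reply is that the trial does what its rationale asks. The preliminary results call for supplementation at admission, early is undefined and may simply mean at admission, and randomisation balances time since onset in expectation. All of this stands: the comparison of zinc started at admission with standard of care is valid without any onset data.

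Four stronger readings are tempting, and the documents do not support them.

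- *The plan's evidence ties zinc's benefit in general to the first 24 hours.* The condition is stated once, for the common cold. The support cited from hepatitis B and C, from elderly people and from the team's 249-patient cohort carries no such window.
- *Onset is never recorded.* Visit 1 takes a medical history, which may capture it. What can be said is that recording it is not specified.
- *The planned guideline (D1) needs results split into early and late starters.* It concerns patients admitted to hospital, which is the population randomised.
- *Power collapses because only early starters can benefit.* The planned 3 days is the difference between arms over all enrolled patients. Scaling it down replaces the plan's hypothesis with another, and the fix would recover none of that loss.

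It can also be said that singling out this one covariate is a matter of preference and that its gain is unknown. That is fair, and it is why the point is a cheap improvement. It does not rescue the Limitation paragraph, whose inference is unsound whether or not onset is recorded.

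**Conclusion.** The point holds as a cheap improvement to precision and interpretation; it is not a flaw in validity. The plan does not specify recording or using time since symptom onset, and it draws from a null result a conclusion that the design cannot support.

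The gain in power for a 3-day difference runs from 0.4 points (r = 0.1) to 10.6 points (r = 0.5) above 77.2%. This rests on 27 evaluable patients per arm, SD 4 days, two-sided alpha 0.05 and a correlation that is purely assumed; error in recalled dates pushes it towards the lower end. The firmer benefit is that the report could describe when in the illness patients were treated and whether the arms were alike. A reader might infer that recording onset would let the trial test early treatment. At 13% to 28% power for a 3-day interaction, it would not.

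**What to change.** Leave eligibility and the start of zinc unchanged.

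1. Add symptom-onset date to the named Visit 1 items, and report days from onset to randomisation by arm in the baseline table.
2. Pre-specify days from onset to randomisation as a continuous covariate in the arm comparisons of days to recovery and IL-6 change. State a simple rule for missing onset dates, for example a single fill-in value computed without regard to arm, so that no patient is dropped. Do not require the covariate for progression.
3. If a treatment-by-onset estimate is wanted, limit it to days to recovery, give its 95% confidence interval and label it exploratory.
4. Reword the Limitation paragraph. A null should be read as no detected benefit of zinc started at admission, at the observed time since onset. It should not be read as showing that low zinc is only a consequence of inflammation, or that earlier supplementation fails.

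The cost is one case-report-form field, one row in the baseline table and a few sentences of analysis plan. The downside is that recalled onset dates are noisy, and some may be missing because patients can enter on a positive test alone or through a surrogate. The onset date should be collected at Visit 1, because later reconstruction is less reliable, and the covariate should be fixed before any outcome data are seen.
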